16.2 Study Populations Definitions

In this study one study population is defined.

The Intent-to-Treat (ITT) population will comprise of all subjects who match the inclusion criteria, have signed their Informed Consent Form and are willing to take-part in the study.

16.3 Analysis Method

IRAS Number: 311621

All data will be anonymised prior to analysis.

The statistical analysis will be done on the ITT population. In case more than 10% of patients present major violations to the protocol (defined as any deviation which may significantly impact the evaluation of the endpoints), primary endpoints analysis will be re-assessed and documented appropriately.

Descriptive statistical data will be used to summarize the characteristics of subjects at the time of inclusion (demographics, baseline and procedure data).

The primary and secondary objectives will be presented as a proportion with 90% confidence intervals (CIs). For other objectives, quantitative variables will be summarized by the number of patients (n), mean, standard deviation (SD) and range; qualitative variables will be summarized by frequency and percentage of patients; rates will be summarized by the numerator, denominator, rate, and its 90% CI. Descriptive statistics only will be provided for AE data.

A complete adverse event description will be done: total number of events and number of patients with at least one of the respective categories AEs, ADEs, SAEs, SADEs, USADEs. Investigation Assessments

17 Participating Investigator and Site

One investigational site in the United Kingdom will be chosen for this study. This will take place at King's College London, in a dedicated research facility which routinely carries out blood sampling related studies.

The Principal Investigator is experienced in the field of phlebotomy and capillary blood sampling and collection. All training on how to use the gentleheel® device will be provided to the Investigator by the Sponsor of the study. A Study Coordinator will be available to ensure the data is collected, and any immediate adverse events noted.

18 Investigation Handling Procedures

The investigational device will be provided to the site by the sponsor. Each device will be entered and tracked on the Device Accountability Log. Once an investigational device is used, it should be discarded per the investigational site's disposal procedure. All devices are one-time use only. The devices should be kept in a secure location, in a cool, dry place.

19 Anticipated Adverse Events

Adverse events that may possibly be caused by, or associated with, the use of the gentleheel® for capillary blood sampling in adult fingertips include:

- Fainting during the incision procedure.
- Pain during and after the incision procedure.
- Bruising.

IRAS Number: 311621

- Hematoma.
- Excessive bleeding requiring more than 5 minutes of compression to stop.
- Infection at the incision site.

20 Anticipated Benefits to the Patients

The anticipated benefits of the gentleheel® for capillary blood sampling in adult fingertips is to improve the user / patient experience of capillary blood collection:

- Ensure collection of an adequate volume of blood from a single finger puncture.
- Minimal discomfort from the procedure blade-based incision devices are less traumatic than needle-based puncture devices (15). The sweeping motion of the tribevel stainless steel blade of the gentleheel® device allows for a smoother and less traumatic incision.
- The gentleheel®'s ergonomic design is easy to use and user friendly.

21 Minimization of Risks

IRAS Number: 311621

This investigation will be monitored to ensure the identification, documentation and analysis of all adverse events, compliance with the Clinical Investigation Plan, the terms of the participating study approval committee to protect the safety and rights of all patients, and applicable local regulations. In addition, risks have been minimized through selection of the Investigator who is experienced in capillary blood sampling.

Although all risks associated with the intended procedure and device may not be fully known at this time, the risks have been identified through an exhaustive literature search and represent the most up-to-date understanding of risks associated with the proposed procedure. The sponsor will employ the following measures throughout the course of this investigation to minimize these risks.

- The Sponsor has clearly defined inclusion and exclusion criteria and will monitor adherence to them, to ensure that only appropriate patients are enrolled.
- The Investigator will obtain informed consent.
- The Sponsor will select the investigational site that has a sufficient level of expertise needed to support and to manage adverse events that could arise and to provide appropriate alternative measures if needed.
- The Investigator will ensure that the follow-up of the patients are consistent with current medical practices and provide the institutional standard of care in line with expert medical judgment.
- The Investigator will report all Safety Adverse Events (SAE).

22 Follow-up of Adverse Events and Adverse Device Effects

Any Adverse Event (AE) or Adverse Device Event (ADE) will be followed until it has resolved, has a stable level of sequelae or in the Investigator's opinion is no longer clinically significant.

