14.1 Primary Objectives

- 1. To determine if a volume of 500 microlitres to 1.1 millilitre of blood can be collected after a single lancing of the fingertip with gentleheel®.
- 2. To assess pain from fingertip lancing with gentleheel®.

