15.6 Procedure

IRAS Number: 311621

After appropriate explanation of the procedure to the patient, he/she will sign the Informed Consent Form to confirm that their participation in the study is voluntary. All required data as per the CRF will be obtained and the patient will then collect blood from 2 incisions on his/her fingertips. No more that a maximum of 4 ml of blood will be collected per patient. The patient will then be asked to rate their pain using the Numerical Pain Rating Scale of 0-10, with 0 being no pain and 10 the worse imaginable pain.

All collected blood samples will be used for volume measurement and discharged afterwards. Following the blood collection from all 2 incisions, the patient will be appropriately monitored, until he/she leaves the investigational site. Any adverse event if presented will be documented before the patient leaves the investigational site.

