16.1 Sample Size

Considering the design and objective of this investigation, the nature of the results needed to conclude on the safety and performance of gentleheel® as incision device for adult fingertips, and the fact that the device is already CE-marked as heel incision device for new-born sampling, the inclusion of 50 subjects in the investigation, a 2 incisions per subject, which will result in 100 blood draws to be assessed, appears therefore sufficient to obtain conclusive findings. This was based on the precision of the 90% CI for the primary objectives as this is a single-arm study. Under this approach, no statement of power is required and alpha = 0.10 will be used as the CI specified as a two-sided 90%.

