22.1 Adverse Events and Device Deficiency Recording on the CRF

All AE must be reported for each patient with a full description, including the nature, the date of onset and resolution, the determination of seriousness, the severity, the action taken, the corrective treatment and the relationship to the device and/or procedure assessed by the Investigator. All investigational device deficiencies will be documented on the CRF and reported to Sponsor.

23 Protocol Synopsis

Title of the investigation: Evaluation of the GRI gentleheel® incision device for adult blood sampling Intended Use Extension				
Objective:	The objective of the proposed clinical investigation is to evaluate the safety and performance of the gentleheel® incision device for capillary blood sampling in adults' fingertips.			
Intended Use:	The gentleheel® device as a fingertip incision device intended for blood sampling in adults.			
Investigational Device:	gentleheel® model Toddler, Blue Incision depth 2.00 mm Incision length 3.00 mm			
Investigation Design:	Prospective, interventional, non-randomized, single-centre			
Participating Sites:	1 site in the UK			
Planned Number of Patients:	50 patients			
Sample size	100 blood draws, 2 finger incisions per patient			
Participation Duration:	Procedure: 20 minutes Follow-up: 5 days (Telephone Call)			
Total estimated duration of the investigation:	1 Month			
Outcomes:	Primary Objectives:			
	 Determine the capillary blood volume collected after a single lancing of the fingertip. Assessment of pain during finger incision using the 0-10 Numerical Pain Rating Scale Secondary Objectives: Adverse events. 			
Inclusion Criteria:	Subjects older than 18 years (adults)Subjects able to provide informed consent			

Exclusion Criteria:

- Subjects younger than 18 years
- Subjects unable to provide informed consent
- Subjects with cognitive impairment which is sufficient to adversely affect the participants understanding of the study, their ability to respond to patient questionnaires or their ability to cooperate with post-procedure assessment.
- Subjects who may be dehydrated
- Subjects diagnosed with poor peripheral circulation from other causes
- Subjects who present with a callus, skin ulceration, or blister at the intended puncture site
- Subjects with thrombocytopenia and/or Platelet abnormalities
- Subjects diagnosed with peripheral edema. Pregnancy or breastfeeding (self-reported)
- Confirmed or suspected malignant cancer

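### Section 16.3 prescribes a proportion for the primary pain endpoint, a 0-10 score with no cut-off, and leaves the summary that fits it to other objectives that do not exist

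*Protocol*

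**What the plan says.** Section 14.1 lists two primary objectives. The first carries numbers: "To determine if a volume of 500 microlitres to 1.1 millilitre of blood can be collected after a single lancing of the fingertip with gentleheel". The second carries none: "To assess pain from fingertip lancing with gentleheel". The synopsis (section 23) words them as "Determine the capillary blood volume collected after a single lancing of the fingertip" and "Assessment of pain during finger incision using the 0-10 Numerical Pain Rating Scale". The only secondary objective, in section 14.2 and in the synopsis, is adverse events.

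Section 15.6 says how pain is measured: "The patient will then be asked to rate their pain using the Numerical Pain Rating Scale of 0-10". Sections 15.5 and 15.6 define only the two ends of the scale. Table 1 in section 15.3 has one pain entry and one volume entry per incision, so each subject contributes two of each.

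Section 16.3 then sets the form of analysis: "The primary and secondary objectives will be presented as a proportion with 90% confidence intervals (CIs"). It continues: "For other objectives, quantitative variables will be summarized by the number of patients (n), mean, standard deviation (SD) and range". Section 16.1 rests the 50 subjects on the precision of the confidence interval for the primary objectives and adds that "alpha = 0.10 will be used as the CI specified as a two-sided 90" per cent interval.

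**The concern.** A proportion needs a numerator. For volume, section 14.1 supplies a range from which one can be formed. For pain, nothing in the protocol says which scores count, so the prescribed statistic is not defined. The same paragraph names a summary that would suit a 0-10 score but gives it to a class of objectives with no members.

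This is more than a detail left for a statistical analysis plan. The protocol chooses a form of analysis, and that form does not fit the endpoint. A later plan that reported mean pain as the primary result would depart from the sentence. One that kept a proportion would need a definition for which the protocol gives no basis.

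The study has a single arm and, by section 15.2, no blinding. Section 20 lists minimal discomfort among the anticipated benefits. If the cut-off were settled once scores were visible, the same data could be presented as well or poorly tolerated.

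**Working it through.** **Fit of rule to endpoint**

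| Objective | Status | Recorded as | Threshold in protocol | Form under 16.3 |
|---|---|---|---|---|
| Volume | primary | µL per incision | 500 µL to 1.1 mL | proportion, can be formed |
| Pain | primary | 0-10 per incision | none | proportion, of what is not stated |
| Adverse events | secondary | events, patients | not needed | proportion |
| Other | none listed | – | – | n, mean, SD, range |

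**The plan's own figures.** Alpha 0.10 two-sided gives z = 1.645, which agrees with a 90% interval. The sample size of 50 cannot be reproduced, because no target half-width, expected proportion or SD is stated. Working backwards at p = 0.5, n = 1.645² × 0.25 / h², which gives 68 for h = 10 points and 106 for h = 8 points. Neither is 50 or 100.

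**Precision of a proportion.** Half-width = 1.645 × √(p(1 − p)/n), at p = 0.5:
- 50 subjects, or 100 scores perfectly correlated within subject: 1.645 × √(0.25/50) = 11.6 points.
- 100 scores treated as independent: 1.645 × √(0.25/100) = 8.2 points.
- Assumed within-subject correlation 0.5: effective n = 100/1.5 = 66.7, half-width 10.1 points.

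**Sensitivity to the cut-off.** The protocol gives no pain mean or SD, so these distributions are assumptions. A normal with mean 3 and SD 2, rounded to whole scores, has P(score ≤ c) = Φ((c + 0.5 − 3)/2):
- c = 2: Φ(−0.25) = 40%
- c = 3: Φ(0.25) = 60%
- c = 4: Φ(0.75) = 77%

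The swing from ≤2 to ≤4 is 37 points. In 50 subjects, with exact 90% limits, this is 20/50 = 40% (28 to 53%), 30/50 = 60% (47 to 72%) and 39/50 = 78% (66 to 87%).

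A different discretisation, with the normal density rescaled over the integers 0 to 10, gives 38%, 58% and 77%, a swing of 39 points. That version has actual mean 3.17 and SD 1.83.

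Other assumed centres, rounded as above:
- Mean 2, SD 1.5: 63% at ≤2 and 95% at ≤4, a swing of 32 points.
- Mean 4, SD 2: 23% and 60%, a swing of 37 points.

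**Precision of the mean, which needs no cut-off.** Half-width = 1.645 × SD/√n. With n = 50:
- SD 1.5: ±0.35
- SD 2: 1.645 × 2/7.07 = ±0.47
- SD 2.5: ±0.58

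At SD 1.83 it is ±0.43. If all 100 scores were independent, SD 2 would give ±0.33. Allowing for two scores per subject, the value lies between ±0.33 and ±0.47.

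**The case against.** Four points on the other side have force.

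- A reader might infer that a 0-10 score cannot be presented as a proportion at all. That goes too far. One can give the proportion at or below every score, each with its interval, and need no single cut-off. The fault is that section 16.3 does not say which proportion is meant.
- A reader might infer that the cut-off will be chosen after the data are seen. The document does not show that. An analysis plan not at hand could fix it beforehand. What stands is that the protocol's own rule does not fit the endpoint, and that nothing in the protocol removes the risk.
- A reader might extend the point to volume, or take the synopsis to name mean volume as an outcome. It does not: the synopsis speaks of the volume collected, and section 14.1 gives a range from which a proportion can be formed. What remains for volume is narrower: no quantitative summary is clearly assigned to it.
- Section 16.3 also promises descriptive statistics for procedure data, which might be read to cover pain and volume. That sentence concerns subject characteristics at the time of inclusion, so the reading is doubtful. It is still enough to rule out saying that mean pain would never be reported.

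The study also sets no pain hypothesis or success rule, and the raw scores are kept, so any summary remains possible later. That limits the severity. It does not supply the missing definition. The 37 to 39 point swing compares different quantities computed from one distribution. It measures how much the definition matters, and it is not an error in a single estimate.

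**Conclusion.** The point holds for pain. Section 16.3 prescribes a proportion for a primary endpoint that is a 0-10 score, without defining the proportion, and gives the fitting summary to objectives that do not exist. As written, the primary pain result is undefined.

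If one cut-off is used, moving it from ≤2 to ≤4 changes the reported proportion by 37 to 39 points, against a 90% CI half-width of about 8 to 12 points. The choice of cut-off would then outweigh sampling error. The swing rests on assumed scores with mean about 3 and SD about 2; with an assumed mean of 2 and SD 1.5 it is 32 points. Late choice of the cut-off is a risk and not an established fact.

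This should be fixed. It does not invalidate the study, because the data collected support a proper analysis.

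**What to change.** Rewrite the section 16.3 sentence endpoint by endpoint.

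- **Pain:** report mean (SD), median and range of the 0-10 score, with a 90% CI for the mean that allows for two scores per subject. One way is to average the two scores within each subject; another is a model with a subject effect. Give any pain proportion only as support, with one cut-off and the unit (subject or incision) fixed before the first subject. The alternative is to show the full cumulative distribution of scores.
- **Volume:** keep the proportion reaching the volume stated in section 14.1, with its 90% CI, and add a quantitative summary (mean or median with a 90% CI), since the synopsis states the outcome as the volume collected.
- **Other objectives:** delete the reference, or say which variables it covers.

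The cost is protocol wording and slightly more analysis. Table 1 already collects the data, and neither the sample size nor the procedure changes.

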22.1 Adverse Events and Device Deficiency Recording on the CRF

All AE must be reported for each patient with a full description, including the nature, the date of onset and resolution, the determination of seriousness, the severity, the action taken, the corrective treatment and the relationship to the device and/or procedure assessed by the Investigator. All investigational device deficiencies will be documented on the CRF and reported to Sponsor.

23 Protocol Synopsis

Title of the investigation: Evaluation of the GRI gentleheel® incision device for adult blood sampling Intended Use Extension				
Objective:	The objective of the proposed clinical investigation is to evaluate the safety and performance of the gentleheel® incision device for capillary blood sampling in adults' fingertips.			
Intended Use:	The gentleheel® device as a fingertip incision device intended for blood sampling in adults.			
Investigational Device:	gentleheel® model Toddler, Blue Incision depth 2.00 mm Incision length 3.00 mm			
Investigation Design:	Prospective, interventional, non-randomized, single-centre			
Participating Sites:	1 site in the UK			
Planned Number of Patients:	50 patients			
Sample size	100 blood draws, 2 finger incisions per patient			
Participation Duration:	Procedure: 20 minutes Follow-up: 5 days (Telephone Call)			
Total estimated duration of the investigation:	1 Month			
Outcomes:	Primary Objectives:			
	 Determine the capillary blood volume collected after a single lancing of the fingertip. Assessment of pain during finger incision using the 0-10 Numerical Pain Rating Scale Secondary Objectives: Adverse events. 			
Inclusion Criteria:	Subjects older than 18 years (adults)Subjects able to provide informed consent			

Exclusion Criteria:

- Subjects younger than 18 years
- Subjects unable to provide informed consent
- Subjects with cognitive impairment which is sufficient to adversely affect the participants understanding of the study, their ability to respond to patient questionnaires or their ability to cooperate with post-procedure assessment.
- Subjects who may be dehydrated
- Subjects diagnosed with poor peripheral circulation from other causes
- Subjects who present with a callus, skin ulceration, or blister at the intended puncture site
- Subjects with thrombocytopenia and/or Platelet abnormalities
- Subjects diagnosed with peripheral edema. Pregnancy or breastfeeding (self-reported)
- Confirmed or suspected malignant cancer
- Anxiety with needles or finger pricks
- History of blood borne infection (e.g., HIV, hepatitis B or C, syphilis, malaria, babesiosis, brucellosis, leptospirosis, arboviral infections, relapsing fever, T lymphotropic virus Type 1, Creutzfeldt-Jakob disease)
- Currently participating in another study
- Donation or loss of 400 mL or more of blood within 4 weeks prior to the start of the study
- Any other condition that in the Investigator opinion may negatively influence Subject's participation in the study
- Intake of medicines that affect blood coagulability (including anticoagulants such as vitamin K, antivirals and anticoagulants such as heparin, aspirin, thrombin inhibitors, vitamin K antagonists)

24 General Study Conduct

24.1 Ethical and Regulatory Considerations

The study will be performed in accordance with the standard ISO 14155 on clinical investigations with medical devices on human subjects and recommendations guiding physicians in biomedical research involving human subjects adopted by the 18th World Medical Assembly, Helsinki, Finland, 1964 and later revisions.

The Clinical Investigational Plan, Informed Consent Form, any other specific study documents and all amendments to these study documents will be reviewed and approved by the appropriate Ethics Committees (ECs) and Competent Authority (MHRA) before enrolment of any patients. In addition, the Sponsor will keep the regulatory authorities informed of any SAEs throughout the study course.

24.2 Data collection, Data handling, Monitoring

The Investigator and the investigational site will permit authorized personnel to review (monitor) completed CRFs, approval committee decisions, and investigator and clinical site records throughout the course of the study. Additionally, patient charts and clinical records will be reviewed by the Sponsor and/or designee(s) so that protocol adherence and source documentation can be verified. All data will be appropriately anonymised.

The subjects will be identified in the CRFs only with a patient number. The subject will be informed that his/her data will be stored and analyzed by computer, that national regulations for handling of computerized data will be followed and that only the Investigator and representatives of the Sponsor will have access to individual subject data. Furthermore, the patients should be informed about the possibility of inspection of relevant parts of the records by the Investigator and/or Health Authorities.

Data collected on the CRFs shall be entered into a database. Accuracy of data entry shall be verified by Data Management staff and monitors. Any inconsistencies observed on data (missing values, failed logic controls) or any discrepancies between data filled and source data on site will generate queries to be answered by the Investigator. Once all queries are answered and data fully corrected, the database will be frozen and access to database will be retired to the Investigator and it will be impossible to perform any additional changes on stored data. Export of the database will then be programmed and accomplished to allow the statistical reporting on a cleaned and validated database. Access to the database shall be limited to appropriate personnel in order to preserve data integrity.

24.3 Record Retention

The Investigator must retain records for this investigation for a minimum of 10 years.

24.4 Device Accountability

IRAS Number: 311621

The Investigator is responsible for ensuring that investigational devices are kept in a secure location and are available only to authorized personnel who are part of the research team for this investigation. The accountability of each investigational device will be documented.

